12.4.2 Missing data

As noted in [Section 5.5](#), any lesions removed from the trial due to the “early exit strategy” will be considered to be treatment failures – non-arrest of the lesion and presence of pain and/or infection requiring removal of the tooth from the study – and not considered to be missing data.

The primary method for handling missing data will be to use a multiple imputation analysis, with imputations based on race/ethnicity, gender, age, trial site, initial ICDAS score, tooth location, treatment, and most recent prior visit results will be performed. Twenty-five imputed datasets will be created, and results will be combined using standard methods.

A sensitivity / tipping point analysis will also be performed to evaluate the MAR (missing at random) assumption for the missing primary efficacy outcome (caries arrest at approximately 6 months). A pattern-mixture approach to the missing data imputation (missing not at random, MNAR) will be applied to the logistic regression model used for imputing the missing caries arrest at approximately 6 months outcome from the variables described above. To represent MNAR, a range of shift parameters will be used to adjust the log odds ratios for the SDF-treated group. The tipping point will be identified as the amount of shift needed to change the statistical significance of the treatment comparison using the primary efficacy analysis. The size of the shift required to change the statistical significance will be used to gauge the plausibility of the MAR assumption.

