6.2.2. Per Protocol (PP) Population

The PP Population will be limited to subjects who complete the baseline, 3-month, and 6-month dental examinations within the originally-specified windows. The PP Population will be used for supportive analyses of efficacy.

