6.11. Efficacy Analyses

All efficacy endpoints will be analyzed using the ITT and ITT2 populations. Additional analyses will be performed on the PP and PP2 populations.

The null hypothesis is no difference between the treatment groups and the alternative hypothesis is there is a difference between treatment groups. All statistical comparisons will be made using a two-sided test. The interim and final analyses will be conducted using p-value thresholds of 0.000001709 and 0.00099938, respectively. The overall type I error for interim and final primary endpoint analysis is two-sided $\alpha=0.1\%$.

Several categorical variables that are to be used as covariates in the GEE model will have categories collapsed due to small sample sizes. Race and ethnicity will be combined to form a single combined variable defined as: Hispanic or Latino if a subject indicated as such for ethnicity, multiracial if more than one race was selected, Black, White, “Asian or ‘American Indian or Alaska Native’ or ‘Native Hawaiian / Other Pacific Islander’”, “Not Reported” or Unknown”. Within the ‘tooth’ variable, lower incisors (LL1, LL2, LR1, LR2) will be combined into a single category and LR6 will be combined with LR5 for the imputation models for the lesion arrest outcomes, and combined into upper jaw / lower jaw and anterior teeth (upper and lower central incisors, lateral incisors, and canines) / posterior teeth (upper and lower molars on the) variables for the imputation models for the presence of tooth pain outcomes. For the imputation models for the presence of tooth pain outcomes, child ages 1 and 2 years will be combined.

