The primary method for handling missing data for 6-month and 8-month efficacy analysis will be to use a multiple imputation analysis. Missing data follow a non-monotone missing pattern. The imputation will use fully conditional specification (FCS) methods. Imputations for lesion arrest and lesion pain will be based on race/ethnicity, gender, age, trial site, initial ICDAS score, tooth location, and lesion arrest results from prior visits using a logistic regression model. Imputations for the subject-level pain score and family outcomes will be based on race/ethnicity, gender, age, trial site, maximum initial ICDAS score for the subject, a non-arrested/arrested indicator for the subject (non-arrested if any of the subject’s study lesions are not arrested) at the ‘current’ visit or at the most recent prior visit if the ‘current’ visit is missing, and results at prior visits for the

outcome using a predictive mean matching model. Missing at random (MAR) will be assumed. Twenty-five imputed datasets will be created, and results from the analyses performed on each imputed dataset will be combined using standard methods via Proc MIAnalyze.

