6.11.2. Primary Outcome Estimand

Estimand attributes for the primary efficacy analysis are defined according to the following attributes specified in ICH E9(R1) Addendum:

- **Treatment** – 38% percent Silver Diamine Fluoride (SDF) applied once at baseline.
- **Population** – Children between 12-71 months of age at baseline, up to the day the child turns 6 years old with S-ECC [*defined as: In children younger than age 3, any sign (non-cavitated or cavitated lesion) of caries in any tooth surface (i.e., most common for this age group will be on erupted smooth surfaces). From ages 3 through 5, ≥ 1 dmfs in maxillary anterior teeth; or a dmfs score of ≥ 4 (age 3), ≥ 5 (age 4), or ≥ 6 (age 5) constitutes S-ECC. Note: The “d” component of the dmfs index is defined as including cavitated and non-cavitated lesions, thus ICDAS>1] and with at least one SDF-target tooth with soft cavitated caries lesions extending into dentin [ICDAS 5 or 6 (Protocol Appendix A)]; and/or cavitated lesion(s) that allow for direct hardness assessment and application of SDF (microbrush applicator must fit the cavity and be able to access all exposed dentin).*
- **Primary Variable** – Number of arrested cavities at the 6-month visit.

- **Population level summary** – Odds Ratio comparing odds of arrested cavities in the treated group vs odds in the placebo group at month 6 visit. Population risk difference at month 6 along with its 95% confidence intervals will also be presented.
- **Intercurrent event (IE)** – Study discontinuation before 6 months visit due to pain (early exit).
- **Strategy** – The following strategy will be used to account for IEs - any efficacy data collected after the occurrence of the intercurrent event (early exit due to pain before visit at month 6) will be set to failure i.e. any lesions removed from the trial due to the “early exit strategy” will be considered treatment failures – non-arrest of the lesion and presence of pain and/or infection – and thus will not be considered to be missing data.

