6.11.3. Primary Efficacy Endpoint: Sensitivity Analyses

Tipping Point Analyses:

A sensitivity / tipping point analysis will also be performed to evaluate the MAR assumption for the missing primary efficacy outcome (caries arrest at 6 months). A pattern-mixture approach to the missing data imputation (missing not at random, MNAR) will be applied to the logistic regression model used for imputing the missing caries arrest at 6 months outcome from the variables described above. To represent MNAR, a range of shift parameters will be used to adjust the log odds ratios for the SDF-treated group. The tipping point will be identified as the amount of shift needed to change the statistical significance of the treatment comparison using the primary efficacy analysis. The size of the shift required to change the statistical significance will be used to gauge the plausibility of the MAR assumption.

Additional Sensitivity Analysis (Visit Windows):

Due to the COVID-19 pandemic and associated illnesses, precautions, and shutdowns, some study subjects were unable to be seen for in-person visits within the study windows. The primary analysis will be repeated using wider windows after the 6-month visit, 7-month intermediate contact, and 8- month visit as follows:

- additional 10 days prior to the original window opening for all visits and intermediate contacts
- additional 10 days after the original window closure for all intermediate contacts
- 6-month visit occurred within the standard window
 - use standard windows for the 7-month contact and 8-month visit
- 6-month visit window expanded to include days +202 through +242 post-baseline in addition to the standard window
 - if the 6-month visit occurred within the expanded window, the 7-month window used 20- 40 days from the 6-month visit, and the 8-month window used 41-79 days from the 6- month visit,
 - if the 6-month visit was completed but was more than 242 days post-baseline, the 7- month window used 20-40 days from the 6-month visit, and the 8-month window used 41-79 days from the 6-month visit
- 6-month visit missed
 - 7-month window 200-270 days post-baseline, 8-month window 221-300 days post-baseline

The wider window for the 6-month visit still falls within a reasonable range for a 6-month recall visit in a clinical setting. Data collected outside the allowable visit or contact windows will be treated as missing data as described above in [Section 6.11.1](#).

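### SAP 6.11 drops randomised treatment from the imputation models, although Protocol 12.4.2 includes it; run as written, the primary SDF-placebo difference generally shrinks toward zero

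*SAP*

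**What the plan says.** SAP 6.11 makes multiple imputation the primary approach to missing 6- and 8-month efficacy data: fully conditional specification, 25 datasets, missing at random. It gives two predictor lists.

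- Lesion arrest and lesion pain are imputed "based on race/ethnicity, gender, age, trial site, initial ICDAS score, tooth location, and lesion arrest results from prior visits".
- For the rest, "Imputations for the subject-level pain score and family outcomes will be based on race/ethnicity, gender, age, trial site", to which it adds the child's worst baseline severity score, an arrested/non-arrested indicator and earlier values of the same outcome.

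Neither list contains treatment. Protocol 12.4.2 has the same core list, but it ends "initial ICDAS score, tooth location, treatment, and most recent prior visit results will be performed". The SAP does not say that imputation is run separately by arm. Its Section 9 lists six changes from the protocol, and this is not one of them.

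The completed data go into a GEE that compares arms (SAP 6.11.1). SAP 6.11.2 summarises the result as "Odds Ratio comparing odds of arrested cavities in the treated group vs odds in the placebo group at month 6 visit", together with a risk difference. The tipping-point analysis in SAP 6.11.3 works by "imputing the missing caries arrest at 6 months outcome from the variables described above", and in it "a range of shift parameters will be used to adjust the log odds ratios for the SDF-treated group".

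**The concern.** An imputation model that leaves out the variable whose effect is being estimated assumes that this effect is zero given the other predictors. Randomisation balances the baseline predictors, so treatment can reach the imputed values only through earlier arrest results. SAP 6.11 itself describes the missingness as non-monotone, so a 3-month result cannot be taken for granted in every child without a 6-month one. Observed lesions, and lesions counted as failures under the early-exit rule, are unaffected.

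At stake are the primary odds ratio and risk difference, the two key secondary endpoints, and power at a final threshold of 0.00099938. The tipping-point analysis inherits the problem: its zero-shift case is the same model without treatment.

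A linked gap appears in both documents. The lesion-level imputation has no term for the child, while the GEE treats a child's lesions as correlated. This acts on standard errors in the opposite, anti-conservative direction, so it matters once treatment is restored.

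**Working it through.** **Inputs.** From Protocol 12.2 and SAP 4: 55% versus 45%, 3 lesions per child, within-child correlation 0.5, 1144 children (572 per arm), final p-value threshold 0.00099938 (z = 3.29). Protocol 12.2 anticipates 10% attrition. Assumed: whole children missing at random, equally by arm; missing rates of 20% and 30%; final look only.

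**The plan's own figure.** Two proportions at two-sided 0.001 and 80% power need 852 lesions per arm. The design effect is 1 + 2 × 0.5 = 2, so 852 × 2 / 3 = 568 children per arm, or 1136 in total for a fixed design. With the stated interim and futility boundaries, 1144 children give 80.1% power. The 1144 therefore reproduces, with all children contributing.

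**Point estimate.** Let f be the share of children missing at 6 months, a the share of those with a 3-month result, φ the correlation between a lesion's 3- and 6-month status, and d3 and d6 the effects at each visit. Without treatment in the model:

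estimate = (1 − f)·d6 + f·a·φ·d3

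**Case 1: no 3-month result (a = 0).** Put u = 2 × 0.2475 / (572 × 3), the variance of the difference if lesions were independent.

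- Complete case: variance 2u / (1 − f).
- SAP as written: reported variance u[2(1 − f) + f + 1.04f], true variance u[2(1 − f) + 0.04f]. The 1.04 is 1 + 1/25, for 25 imputations.
- Odds ratio: [(0.5 + d/2) / (0.5 − d/2)]², with d the attenuated difference; 1.49 with no attenuation.

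| Missing | Difference (points) | Odds ratio | Power, SAP list | Power, complete case |
|---|---|---|---|---|
| 10% | 9.0 | 1.43 | 68.3% | 74.5% |
| 20% | 8.0 | 1.38 | 51.5% | 66.8% |
| 30% | 7.0 | 1.32 | 32.3% | 57.6% |

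Under the null, the rejection rate is 0.05%, 0.02% and 0.01%, below the nominal 0.1%.

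**Cases 2 and 3: half, or all, of the missing children have a 3-month result.** Equal effects at 3 and 6 months are assumed, in line with the stability hypothesis in Protocol 12.1. Each cell gives φ = 0.5, then φ = 0.8 (both assumed). Power is simulated: latent-normal lesions, 25 imputations, Rubin's rules, 1000 replicates, error about 1.5 points, correlation between different lesions across visits assumed at 0.40 and 0.48. The comparator imputes whole children within arm.

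| Missing | Half: difference | Half: power, SAP list | Half: power, within arm | All: difference | All: power, SAP list | All: power, within arm |
|---|---|---|---|---|---|---|
| 10% | 9.25; 9.4 | 71.6; 75.0% | 76.0; 77.9% | 9.5; 9.8 | 75.4; 75.8% | 77.3; 76.7% |
| 20% | 8.5; 8.8 | 58.5; 65.3% | 68.7; 71.7% | 9.0; 9.6 | 69.1; 76.6% | 72.6; 77.6% |
| 30% | 7.75; 8.2 | 42.9; 55.0% | 60.8; 67.5% | 8.5; 9.4 | 59.3; 71.9% | 65.3; 73.3% |

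Power should be compared only within a case. Simulating case 1 gives 70.9, 50.1 and 33.9% for the SAP list and 77.7, 67.5 and 59.3% for complete cases, somewhat different from the closed form.

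**Unequal effects.** With a = 1 and 10% missing, a 3-month effect of 5 or 15 points gives 9.25 or 9.75 points at φ = 0.5, and 9.4 or 10.2 at φ = 0.8. The last exceeds 10 because φ·d3 = 0.8 × 15 = 12 is larger than d6.

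**Larger true effect, 65% versus 45% (assumed), case 1.** Missing lesions are drawn at the pooled 55%, so 20 points becomes 18, 16 and 14, and the odds ratio falls from 2.27 to 2.09, 1.92 and 1.77. Power stays above 99.8%.

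**Treatment added, no child term, case 1.** Reported variance is u[2(1 − f) + f + 1.04(f²/(1 − f) + f)]; true variance is u[2/(1 − f) + 0.04(f²/(1 − f) + f)]. The ratio of standard errors is 0.951, 0.906 and 0.864, so they are about 5%, 9% and 14% too small.

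**Separate check.** A simulation of logistic fully conditional imputation, with latent 3-to-6-month correlation 0.5 or 0.9, lost 0.3 to 1.0 points at 10% missing and 0.8 to 2.8 at 30% with treatment omitted. With treatment included, the result stayed within about 0.2 points of the complete-data value. A null run showed no apparent bias.

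**The case against.** The SAP list may simply be incomplete. The SAP says that it is based on the protocol, Section 9 records no removal of treatment, and the tipping-point text presupposes that arm is available.

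The size may also be modest. Case 1 is the extreme. The stated 10% attrition covers all 8 months, so from attrition alone it is an upper figure at 6 months. If arrest is as stable as the protocol hypothesises, φ should be high: at 55% arrested, φ = 0.5 means that 1 − (0.55 + 0.5 × 0.45) = 22.5% of arrested lesions revert, against 9% at φ = 0.8. With φ = 0.8, 10% missing and all 3-month results available, the estimate is 9.8 points (odds ratio about 1.48 against 1.49). Even the 1-point loss in case 1 is about 0.4 of the 2.5-point standard error.

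There is a partial safeguard. The per-protocol set is "limited to subjects who complete the baseline, 3-month, and 6-month dental examinations within the originally-specified windows", and "Additional analyses will be performed on the PP and PP2 populations", so those results need little 6-month imputation. The effect on the key secondaries is not quantified, and 8-month arrest can also draw on the 6-month result. Finally, the missing child term is a separate matter, not a conflict between the documents.

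Most of this stands as a limit on size and direction. It does not remove the fault. A programmer who follows two detailed lists imputes without treatment. The tipping-point shift is a sensitivity parameter and does not put treatment into the primary model. The per-protocol analysis is only supportive. SAP 6.4.2 says that COVID-19 kept some children from in-window visits but gives no count, so 10% cannot be taken as a ceiling. The child term belongs in the same edit because restoring treatment alone would exchange a conservative error for an anti-conservative one.

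**Conclusion.** The SAP is wrong as written. Its primary missing-data model departs, undeclared, from Protocol 12.4.2 and does not match the GEE that compares arms. For the planned effect the primary difference loses between 0.2 and 1.0 points at 10% missing and between 0.6 and 3.0 at 30%, depending on how many missing children have a 3-month result and how strongly the two visits correlate. At 10% missing with all 3-month results present, the power loss is within simulation error.

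These ranges assume children missing at random and equally by arm, equal effects at 3 and 6 months, and φ of 0.5 to 0.8. The pull is toward zero unless a·φ·d3 exceeds d6. With no effect at either visit there is no bias. A large true effect protects power but not the estimate.

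**What to change.** In SAP 6.11, state that randomised treatment is a predictor in every imputation model (arrest, pain and subject-level scores), or that imputation is run separately by arm. In the same edit, keep within-child correlation in the lesion-level imputations, for example by using the arrest status of the child's other lesions or a two-level imputation. Run the tipping-point shifts from that model. List in Section 9 any remaining difference from Protocol 12.4.2.

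The cost is SAP wording, a few lines of code and a somewhat more complex imputation model. No new data are needed.

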4. SAMPLE SIZE

The population will be children 12-71 months of age at the baseline caries examination attending early childhood education programs or recruited from clinics associated with the Michigan, Iowa or New York clinical trial sites.

The primary outcome of this trial is the proportion of arrested caries lesions approximately 6 months from the baseline visit (i.e., lesions that have changed from soft to hard over the trial period according to the ICDAS II activity criteria). A 10% difference in the proportion of arrested caries lesions between the SDF and placebo groups will be considered clinically significant. Prior studies in the literature of SDF using this outcome in primary cavitated lesions have shown a wide range for the proportion of arrested caries lesions for both SDF-treated and placebo-treated or untreated lesions; therefore the 10% difference in proportions was calculated assuming 55% versus 45% arrested caries lesions for SDF compared to placebo. In prior studies, an average of 4 lesions was treated per participant, with a within-participant correlation of 0.5; we are conservatively assuming 3 lesions per participant. The sample size calculations used a 2-sided test for a difference in proportions with cluster randomization (participant as the cluster) at significance level $\alpha=0.1\%$, with 80% power to detect a superiority difference of 10% for SDF compared to placebo. The calculations also account for the use of an early stopping rule for efficacy and futility. The interim analysis will be performed after approximately half of the sample has completed the 6-month examinations. A Lan-Demets spending function with an O'Brien-Fleming type boundary will be used, with p-values for efficacy at 0.000001709 and 0.00099938 at 50% and 100% completion, respectively. Non-binding p-values for stopping due to futility at 50% and 100% completion will be 0.2336928 and 0.00099938, respectively. With the above assumptions, the trial will require 1144 participants to be enrolled. Sample size calculations were made using East version 6.

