6.1. Statistical Comparisons

All statistical comparisons will be made using a two-sided test. The interim and final analyses will be conducted using p-value thresholds of 0.000001709 and 0.00099938, respectively, for the primary analysis. The overall type I error for interim and final primary endpoint analysis is two-sided $\alpha=0.1\%$.

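### With 25 imputations and no fixed seed, a pooled p-value close to either efficacy threshold is not reproducible; more imputations would fix this at almost no cost

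*SAP*

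**What the plan says.** SAP 6.11 names multiple imputation by fully conditional specification as the primary approach to missing 6- and 8-month efficacy data, and fixes the number: "Twenty-five imputed datasets will be created, and results from the analyses performed on each imputed dataset" are then pooled in Proc MIAnalyze. Protocol 12.4.2 has the same number: "Twenty-five imputed datasets will be created, and results will be combined using standard methods".

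The decision rule is in SAP 6.1 and 6.11: "The interim and final analyses will be conducted using p-value thresholds of 0.000001709 and 0.00099938, respectively". The overall two-sided type I error is 0.1%. SAP 6.11.4 tests the two key secondary endpoints at two-sided 0.1% as well. SAP 6.11.3 defines the tipping point as the shift at which the primary comparison changes significance, so that analysis is read at the threshold by construction.

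Neither document gives a reason for 25, a random seed, a tolerance for Monte Carlo error or an expected fraction of missing information. The one planning figure is 10% attrition (Protocol 12.2). SAP 6.4.2 records that COVID-19 prevented some in-window visits. SAP 6.11.3 treats data outside the allowable windows as missing, without saying how much that is.

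**The concern.** The pooled estimate and its variance both depend on the random draws used to impute, so two runs on the same data with different seeds give different p-values. In the far tail of the distribution a small change in the test statistic is a large relative change in p. The thresholds here correspond to |z| of about 3.29 and 4.79, far beyond the 1.96 of a 5% test.

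If the result falls near a threshold, the efficacy conclusion could depend on a seed that nobody chose in advance. The SAP cites requests from a pre-NDA meeting, so the primary result is meant for regulatory use. It should not be open to the question whether another run would have failed.

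**Working it through.** **Plan's own figures.**
- Boundaries: the Lan-DeMets O'Brien-Fleming-type spending function at half information is 4 × [1 − Φ(z(1 − α/4)/√0.5)]. With α = 0.001 it gives 1.7086 × 10⁻⁶. Numerical integration gives 0.00099936 at the final look. The plan states 0.000001709 and 0.00099938.
- Sample size: 55% versus 45%, two-sided α = 0.001 and 80% power need 852 lesions per arm. The design effect is 1 + (3 − 1) × 0.5 = 2. So 852 × 2/3 = 568 children per arm, 1136 in total, against 1144 stated (0.7% apart). The design alternative therefore corresponds to an expected final z of 3.291 + 0.842 = 4.13.

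**How much information is missing (assumption).** Let λ be the between-imputation share of total variance, which is the fraction of missing information when M is large. It was simulated with 55% versus 45%, 3 lesions per child, intraclass correlation 0.5, whole children missing and lesion-level imputation as in SAP 6.11. The result depends on how much the prior visit is assumed to tell.
- 10% of children missing: λ about 0.02-0.06.
- 20% of children missing: λ about 0.045-0.12.

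**Monte Carlo model of the pooled p-value.** Scale the total variance to 1, so B = λ and U = 1 − λ. For M imputations:
- pooled estimate ~ N(z, B/M);
- estimated between-imputation variance B̂ ~ B × χ²(M − 1)/(M − 1);
- T = U + (1 + 1/M)B̂;
- p from Rubin's t reference, with (M − 1)(1 + 1/r)² degrees of freedom, where r = (1 + 1/M)B̂/U.

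Here z is set so that the p-value without Monte Carlo error lies exactly on the threshold.

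SD of log p (roughly the relative SD of p when small) with M = 25:

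| λ | final 0.00099938 | interim 0.000001709 |
|---|---|---|
| 0.02 | 11% | 16% |
| 0.05 | 18% | 29% |
| 0.06 | 20% | 33% |
| 0.10 | 29% | 49% |
| 0.20 | 48% | 88% |

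A hand check that keeps only the noise in the estimate is SD(z) ≈ √(λ/M) = √(0.10/25) = 0.063. At the final threshold that moves p by −20% or +25% for one SD. The table is larger because it also carries the noise in B̂.

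**More imputations.** SD of log p at λ = 0.05 / 0.10 / 0.20:
- M = 200: 6% / 10% / 16% (final), 10% / 16% / 29% (interim).
- M = 500: 4% / 6% / 10% (final), 6% / 10% / 18% (interim).

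**Error rates at M = 25.** Type I error is 0.000999 and 1.71 × 10⁻⁶ at λ = 0.10, and 0.001003 and 1.77 × 10⁻⁶ at λ = 0.20. Final-look power is 79.9% at λ = 0.05 and 78.9% at λ = 0.20, a loss of about 0.1 to 1 point.

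**Chance that two seeds disagree under the design alternative.** Draw z from N(4.13, 1) at the final look, or N(4.13 × √0.5, 1) at the interim, then impute twice independently. For λ = 0.05 to 0.20:
- Final look: 1.6-4.5% at M = 25, 0.6-1.5% at M = 200, 0.4-0.9% at M = 500.
- Interim: 0.5-1.3% at M = 25, 0.1-0.3% at M = 500. It is low because only about 3% of trials cross that boundary under this alternative.

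**The case against.** A reader might infer that 25 imputations make the test invalid at such small thresholds. The documents do not support that. Pooling is by standard methods, and Rubin's 1 + 1/M term and t reference allow for a finite number of imputations. The calculated type I error stays essentially at its nominal value.

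A reader might also quote one noise figure, say 20% to 70%, for a p-value near either threshold. That would pool two different ranges. At the final threshold, 20% needs λ of about 0.06 and 70% needs about 0.33. At the interim threshold, the same figures need about 0.03 and 0.15. No value of λ is in the documents. Prior-visit arrest results enter the imputation model, and early-exit lesions count as failures, not missing data. Both hold λ down. With the planned 10% attrition, the noise at the final threshold is about 11-20%.

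Nor do the digits in the thresholds claim matching precision in the p-value; they are boundary outputs of the design software. The tipping point serves as a judgement on the plausibility of missing at random, and the blur in it has not been quantified and is probably small.

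Finally, the alternative of 55% versus 45% is modest beside the short-term trial in Protocol 2.2, which saw 72% of cavities turn hard against 5% on placebo. An effect near that size would be nowhere near the boundary.

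All of this stands, and it limits the point to reproducibility of a borderline result. It does not remove the point: the trial was sized with "with 80% power to detect a superiority difference of 10% for SDF compared to placebo", and under that assumption borderline results do occur.

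**Conclusion.** The point holds as a minor one about reproducibility. With 25 imputations and no pre-specified seed, a p-value near a threshold carries a Monte Carlo SD of about 11-20% (final) and 16-33% (interim) if missing information is 2-6%, and about 29-48% and 49-88% if it is 10-20%. Under the design alternative, two seeds would reach opposite final decisions in about 1.6-4.5% of trials for missing information of 5-20%. Type I error is preserved and the power loss is about 1 point or less.

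These sizes rest on an assumed or simulated fraction of missing information, including an assumed correlation with the prior visit. The interim figures also assume that the imputation in SAP 6.11 is used at the interim. SAP section 8 does not say so, but its endpoint is the 6-month outcome to which 6.11 applies. If the observed effect is far from the boundary, the number of imputations will not affect the conclusion.

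**What to change.** In SAP 6.11, and in Protocol 12.4.2 to match:
- Replace 25 with at least 200 imputed datasets, preferably 500. The larger number matters most for the interim and ITT2 analyses: at λ = 0.20 the SD at the interim threshold is still 29% with 200, against 18% with 500.
- Pre-specify the random seed. This makes the run repeatable and removes any choice of seed, but it does not reduce the noise. Only more imputations do that.
- Report the Monte Carlo error of the pooled estimate and of the p-value for the primary, key secondary and tipping-point analyses.

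The cost is computer time. No data collection, sample size or trial procedure changes.
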